7.2.3 Adjustment for Covariates

Adjustment for covariates including the stratification factors BCLC advanced stage C vs. BCLC intermediate stage B and ECOG performance status (0 vs. 1, 2) is planned for secondary endpoints PFS and OS in Cox proportional hazard modeling and logrank testing.

7.2.4 Subgroup Analyses

Subgroup analyses may be performed on the stratification factors BCLC advanced stage C vs. BCLC intermediate stage B and ECOG performance status (0 vs. 1, 2). Subgroup analyses may also be performed on laboratory parameters testing for the hepatitis B surface antigen and the hepatitis C surface antibody (positive for the hepatitis B surface antigen vs. not, positive for the hepatitis C surface antibody vs. not).

7.3 Handling of Dropouts and Missing Data

These rules will apply uniformly to all efficacy analyses based on the BICR assessment as well as efficacy analyses resulting from application of mRECIST for HCC to investigator assessed tumor measurements. For investigator reported outcomes, analyses

will present outcomes reported by the investigator without consideration of missing data or censoring rules. In general, subjects not classifiable under the mRECIST for HCC response categories due to insufficient data or early death will be classified as non-evaluable for objective response, but will be counted in the denominator of all response rate calculations.

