6.5 Concomitant Medications

Concomitant medications will be coded according to drug name as defined in the World Health Organization (WHO) Drug Dictionary, classified according to the Anatomical Therapeutic Chemical (ATC) classification system and presented in tables and listings.

7 Efficacy Analyses

Efficacy analyses will be based on the BICR assessment. Evaluation of efficacy endpoints based on investigator data will be provided by applying modified Response Evaluation Criteria in Solid Tumors for hepatocellular carcinoma (mRECIST for HCC) (Lencioni, 2010 and Llovet, 2008) to investigator assessed tumor measurements. In addition, investigator reported objective response and disease control rates will be summarized with the caveat that these may differ from the application of mRECIST for HCC to the investigator assessed tumor measurements. Investigator reported disease progression dates will be presented in listings but not analyzed using time to event analysis techniques. Instead these analyses will be performed on time to progression (TTP) and progression free survival (PFS) dates resulting from application of mRECIST for HCC to investigator assessed tumor measurements along with the censoring guidelines and missing data rules described in this Analytical Plan.

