7.2 Major Secondary Efficacy Endpoint Analyses

7.2.1 Major Secondary Efficacy Endpoints

Secondary efficacy endpoints include overall survival, progression free survival, objective response, disease control, time to response (for responders), and duration of response (for responders) as defined below:

- Overall survival (OS): time from randomization to death from any cause.
- Progression free survival (PFS): time from randomization to radiologic disease progression or death from any cause.
- Objective response: CR+PR according to mRECIST for HCC.
- Disease control: CR+PR+SD according to mRECIST for HCC.
- Time to response: time from randomization to 1st PR or CR in responders only.
- Duration of response: time from 1st PR or CR to radiologic disease progression; in responders only.

such that CR is complete response, PR is partial response and SD is stable disease.

All secondary endpoints will be based on BICR assessments of imaging scans. Additional analyses based on application of mRECIST for HCC to investigator assessed tumor measurements, or investigator determination of disease response will be performed. For

the purposes of establishing SD based on BICR or application of mRECIST for HCC to investigator assessed tumor measurements, at least 6 weeks from the baseline measurement must elapse without progressive disease (PD) in order to assign a best overall response of SD. Confirmation of PR and CR will occur no fewer than 4 weeks after initial documentation of PR or CR. If PR or CR that is pending confirmation is designated at an assessment followed by 1 or more non-evaluable assessments or assessments of SD, response may be confirmed thereafter.

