7.2.2 Major Secondary Efficacy Analyses

Secondary analyses include estimates, using Kaplan Meier methods, of median PFS and median OS along with associated logrank testing. The hazard ratio will also be estimated for PFS and OS using Cox proportional hazard modeling adjusting for factors stratifying the randomization as covariates. In addition, estimates of overall response rate (CR+PR) and disease control rate (CR+PR+SD) will be reported with 95% confidence intervals and an estimate of the difference in response rates and disease control rates between groups will be reported and tested for significance with a Pearson chi-square test (or Fisher's exact test, as appropriate). The analysis of PFS as determined by the BICR described in this section will be repeated, but with PFS based on application of mRECIST for HCC to investigator assessed tumor measurements. Analyses of TTP as described in Section 7.1.3 will be repeated for PFS. In addition, the analyses of objective response, disease control, time to response and duration of response will be repeated with 2 analyses: 1) with endpoints based on application of mRECIST for HCC to investigator assessed tumor measurements and 2) with endpoints as provided directly by the investigator.

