7.3.2 Other Censoring Rules

Subjects who reach the survival endpoint due to any reason prior to experiencing a radiologic disease progression will be censored for TTP at the date of their last complete disease assessment. Subjects remaining on study without radiologic disease progression or death at the time of analysis will be censored for TTP and PFS at the date of their last

complete disease assessment. Subjects lost to follow-up prior to experiencing a radiologic disease progression or death will be censored for TTP and PFS at the date of their last complete disease assessment.

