7.5 Assignment of Dates of Disease Progression or Disease Response

For all analyses of endpoints as assessed by BICR or by application of mRECIST for HCC to investigator assessed tumor measurements, there may be cases in which disease assessments span a series of dates. For establishing the start date of a subsequently confirmed response in which the disease assessment spans multiple days, the response date assigned will be the latest date of evaluations corresponding to the disease assessment. The date of latest assessment will also be assigned for a mid-study assessment showing SD as the date assigned to that SD for the purposes of censoring duration of SD.

The date of PD will be the 1st date at which any objective diagnostic test provides data indicating PD. Specifically, the date of PD will be the earliest of the following 3 dates:

- Date of PD as indicated by target lesions: if PD is triggered by a change in SLD of target lesions, and all evaluations occurred on the same day, assign that date. If the dates of evaluation of the target lesions vary for the same assessment, assign the first evaluation date among target lesions.
- Date of PD as indicated by non-target lesions: the 1st date for which any non-target lesion exhibits a response of PD.
- Date of PD as indicated by new lesions: the 1st date for which any new lesion is detected.

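### Investigator-reported duration of response is to be analysed with no censoring rule, and SAP 7 bars time-to-event methods for the progression dates it needs, so a response still ongoing at database lock has no valid handling (minor)

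*SAP*

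**What the plan says.** SAP 7.2.1 defines the endpoint: "Duration of response: time from 1st PR or CR to radiologic disease progression; in responders only".

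SAP 7.2.2 states that "the analyses of objective response, disease control, time to response and duration of response will be repeated with 2 analyses". The first repeat applies mRECIST to the investigator's tumor measurements. The second is "with endpoints as provided directly by the investigator".

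SAP 7.3 confines its missing-data and censoring rules to the BICR-based analyses and the mRECIST-derived investigator analyses. For investigator-reported outcomes it says the analyses "will present outcomes reported by the investigator without consideration of missing data or censoring rules".

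The opening text of SAP 7 says of purely investigator-reported results that "investigator reported objective response and disease control rates will be summarized", and then: "Investigator reported disease progression dates will be presented in listings but not analyzed using time to event analysis techniques". Duration of response is not in that list.

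Where the SAP does give censoring for unfinished follow-up, in 7.3.2, it names two endpoints: "Subjects remaining on study without radiologic disease progression or death at the time of analysis will be censored for TTP and PFS". The only duration mentioned with censoring is in 7.5, in the phrase "for the purposes of censoring duration of SD".

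SAP 3 allows lock when 90% of randomized and treated subjects have progressed. It also allows lock once everyone has at least 12 months of follow-up, after a blinded look at the remaining data. Some responses may therefore still be running at lock.

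**The concern.** Duration of response is a time-to-event quantity built from the investigator's progression date. SAP 7.2.2 orders that it be analysed. SAP 7.3 withholds the censoring that a valid analysis of unfinished responses needs, and SAP 7 withholds time-to-event methods for the dates that end it. A programmer cannot produce a valid estimate under 7.2.2 without departing from 7.3 or 7.

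What remains is a choice the SAP does not make. A responder with no progression date can be left out, counted as ended at the last follow-up, or only listed. The first shortens both arms' estimates, and more so where responses last longer, which pulls the comparison toward no difference. The second can do the same when follow-up is short. A responder who dies without progression raises the same question.

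**Working it through.** **The plan's own figures.** The documents state no figure for duration of response. The design figure is 80% power for median TTP of 5.5 versus 8.9 months at one-sided 0.10 (SAP 5.1). It reproduces: HR = 5.5/8.9 = 0.618, and events = 4 × (1.282 + 0.842)² / (ln 0.618)² ≈ 78. It does not enter this point and is not affected by it.

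**Assumed inputs, none of them in the documents.** Exponential durations with true medians m of 6 and 9 months, so λ = ln 2 / m = 0.1155 and 0.0770. Follow-up after response C is uniform on (a, b), in two cases:
- 3 to 18 months, a short case;
- 9 to 21 months, closer to SAP 3 and 4: the 12-month lock minimum and the roughly 24-month study, each less about 3 months to reach response (scans are every 6 weeks).

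**Share still ongoing** = (e^(−λa) − e^(−λb)) / (λ(b − a)).
- 3 to 18: m = 6 gives (0.707 − 0.125)/1.733 = 34%; m = 9 gives (0.794 − 0.250)/1.155 = 47%.
- 9 to 21: m = 6 gives (0.354 − 0.088)/1.386 = 19%; m = 9 gives (0.500 − 0.198)/0.924 = 33%.

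**Reading A: ongoing responders left out.** The median is the t at which the integral from 0 to t of λe^(−λu)·P(C > u) du reaches half of (1 − share ongoing).

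**Reading B: ongoing responses counted as ended at last follow-up.** The median solves e^(−λt)·P(C > t) = 0.5.

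| Follow-up after response | True medians | Reading A | Reading B |
|---|---|---|---|
| 3 to 18 months | 6 vs 9 | 3.5 vs 4.0 | 4.9 vs 6.0 |
| 9 to 21 months | 6 vs 9 | 4.5 vs 5.3 | 6.0 vs 9.0 |

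Under A the true 3-month difference shrinks to about 0.5 month (short follow-up) or 0.8 month (longer). The shorter arm is understated by about 42% or 25% and the longer arm by about 55% or 41%. Under B the difference is about 1.2 months with short follow-up. With 9 to 21 months the medians are unbiased, because no one is cut off before either true median.

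**Other assumptions, Reading A.** With medians of 5.5 and 8.9 months (borrowed from the TTP design) and fixed follow-up of 6, 12, 18 and 24 months, the medians are 2.45 vs 2.65, 3.92 vs 4.65, 4.72 vs 6.07 and 5.12 vs 7.06. The ratio falls from 1.62 to 1.08, 1.19, 1.29 and 1.38. With equal true medians both arms are shortened equally, so no difference is created.

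**With censoring.** Kaplan-Meier with ongoing responses censored returned about 5.5 and 8.9 to 9.0 months in large simulated samples, with follow-up of 4 to 22 or 10 to 22 months.

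**The case against.** The strongest reply is that the SAP nowhere orders a biased estimate. A reader might infer that ongoing responders are dropped. The documents do not say so: 7.3 says only that investigator outcomes are presented as reported, and Reading B or a plain listing fits it equally well. That stands, which is why both readings are worked above.

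A reader might also infer that SAP 7 forbids any analysis of investigator progression dates, in flat contradiction of 7.2.2. It bars time-to-event techniques, not every summary, so a descriptive table is not literally excluded. That stands too. But a descriptive table of completed durations is Reading A, so the narrower wording does not rescue the analysis.

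It can be said that the 3-to-18-month case is short against the 12-month lock trigger. That is fair, and the 9-to-21-month case is the better guide under that trigger. The attenuation under exclusion is smaller there but remains.

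Finally, SAP 7 lists only response and disease control rates for investigator-reported summary, so duration in 7.2.2 may simply be over-inclusive drafting. It may be, and then deletion is the right repair. Few responders are likely: the first cited Phase 3 trial had a 2% partial response rate on sorafenib (Protocol 1.5), which would be 50 × 0.02 = 1 subject in an arm of 50. The documents give no expected rate for this trial. With so few, the comparison says little under any rule.

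**Conclusion.** The point holds as a defect in the wording of SAP 7, 7.2.2 and 7.3 taken together: an ordered analysis has no valid way to treat an unfinished response. It does not hold as a claim that the SAP drops ongoing responders or that a real advantage would be erased. The size of any distortion depends on an unstated programming choice and on follow-up after response. Under the assumptions above it runs from none in the median (Reading B, 9 to 21 months) to a 3-month difference reduced to 0.5 month (Reading A, 3 to 18 months).

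The gap extends beyond the investigator-reported repeat. 7.3.2 names only TTP and PFS, and 7.2.2 states no method for duration of response, so the BICR-based version has no explicit censoring rule either.

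Severity is minor. This is the second supportive repeat of a secondary endpoint, in responders only. Primary TTP, its significance level and its power are unaffected.

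**What to change.** Choose one of two edits in SAP 7.2.2:

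1. Delete duration of response from the investigator-reported repeat, analysis (2). This agrees with SAP 7 and 7.3 as they stand.
2. Keep it and specify Kaplan-Meier, with responders lacking an investigator-reported progression censored at their last complete disease assessment. Then amend the sentence in SAP 7 on investigator progression dates and the sentence in 7.3 on investigator-reported outcomes so that both allow this.

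With either choice, extend 7.3.2 to name duration of response for every source that is kept, including BICR, and state how a death without progression is treated.

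The cost is two or three SAP sentences before unblinding. No new data, sample size or conduct change is needed.

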7.3.1 Handling of Missing Data

7.3.1.1 Missing Data at Baseline

If a subject has missing target lesion measurements at baseline, the subject will be assigned PD if criteria for PD is exhibited at the first disease assessment. Otherwise, the subject will be classified as non-evaluable for objective response and censored at date of randomization for TTP. For PFS the subject will be censored at date of randomization unless the subject dies within the first 6W post-baseline in which case this date will qualify as a PFS event.

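### For subjects with missing baseline target lesions, SAP 7.3.1.1 lets the outcome decide whether TTP and PFS are censored at randomization, so later progressions and later PFS deaths are dropped

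*SAP*

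**What the plan says.** SAP 7.3.1.1 covers subjects whose target lesion measurements are missing at baseline. It has three parts:

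- Progression: "the subject will be assigned PD if criteria for PD is exhibited at the first disease assessment".
- Everyone else, for TTP: "Otherwise, the subject will be classified as non-evaluable for objective response and censored at date of randomization for TTP".
- PFS: "For PFS the subject will be censored at date of randomization unless the subject dies within the first 6W post-baseline"; such a death is a PFS event.

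SAP 7.3 gives the scope: "These rules will apply uniformly to all efficacy analyses based on the BICR assessment". The same sentence extends the rules to the analyses that apply mRECIST to investigator tumor measurements. SAP 7.3 also keeps subjects who cannot be classified for response: they are non-evaluable "but will be counted in the denominator of all response rate calculations".

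Four other places bear on the point:

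- SAP 7.2.1: "Progression free survival (PFS): time from randomization to radiologic disease progression or death from any cause".
- SAP 7.3.1.2: when target lesions are missing at a later scan, progression still counts if another criterion for it is met.
- SAP 7.3.2: subjects without progression or death are censored at their last complete disease assessment.
- SAP 7.5: the progression date is the earliest of a target, a non-target and a new-lesion date. For the last: "Date of PD as indicated by new lesions: the 1st date for which any new lesion is detected".

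The overall response table in Protocol Appendix 5 assigns progressive disease for a new lesion or for non-target progression whatever the target-lesion status.

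**The concern.** Censoring should not depend on the outcome being measured. Here it does. A subject with missing baseline targets who progresses at scan 1 is an event. One who is progression-free at scan 1 gets zero follow-up, even if a new lesion appears at scan 2. For PFS, a death in week 5 counts and a death in week 10 does not. Yet neither a new lesion nor a death date needs a baseline target measurement.

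The affected subjects who stay in the analysis are thus early failures only. That raises the estimated early event rate and discards usable events. If affected subjects were spread unevenly between arms, the hazard ratio would shift as well.

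**Working it through.** **Inputs.** 50 subjects per arm, TTP medians 5.5 and 8.9 months, one-sided 0.10, 80% power (SAP 5.1). Scan interval 42 days (SAP 7.3.1.3), which is 42/30.4375 = 1.380 months. OS medians on sorafenib of 10.7 and 6.5 months in the two placebo-controlled Phase 3 trials (Protocol 1.5). The documents give no share f of subjects with missing baselines; 5%, 10% and 20% are assumptions.

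**The plan's own figure.** HR = 5.5/8.9 = 0.618. Events = 4(1.2816 + 0.8416)²/(ln 0.618)² ≈ 78, and 78 events give power 0.801. The stated 80% is reproduced and is not in dispute.

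**Who is kept.** With exponential times, p = 1 − 2^(−1.380/median). This gives 16.0% at 5.5 months and 10.2% at 8.9 months, or 13.1% on average. If 10 of 100 subjects were affected, split evenly, 5 × 0.160 + 5 × 0.102 ≈ 1.3 would be kept, all as events, and 8.7 censored at day 0.

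**Early event rate, control arm.** The estimate at scan 1 under the rule is p/[(1 − f) + f·p]:

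- f = 5%: 0.1596/(0.95 + 0.0080) = 16.7%
- f = 10%: 0.1596/(0.90 + 0.0160) = 17.4%
- f = 20%: 0.1596/(0.80 + 0.0319) = 19.2%

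The true value is 16.0%. At f = 5% the difference is about 0.35 subject in an arm of 50.

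This gives affected subjects the full chance of visible progression at scan 1. If only half of it were visible without baseline targets (an assumption), f = 5% gives (0.95 × 0.1596 + 0.05 × 0.0798)/(0.95 + 0.05 × 0.0798) = 16.3%, and f = 10% gives 16.7%.

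**Hazard ratio and power for TTP.** Simulation: exponential times, 42-day scans, 24 months' follow-up per subject (assumed), unadjusted log-rank test, one-step HR, 3,000 runs. The comparator censors every affected subject at randomization whatever the outcome. The one-step HR on tied scan times does not return 0.618 exactly, so only comparisons between rows are meaningful.

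| Equal missingness, medians 5.5 vs 8.9 | Events | HR | Power, SAP rule | Power, comparator |
|---|---|---|---|---|
| none | 89.4 | 0.587 | 0.837 | – |
| 5% | 85.5 | 0.586 | 0.828 | 0.823 |
| 10% | 81.7 | 0.587 | 0.817 | 0.822 |
| 20% | 74.1 | 0.585 | 0.783 | 0.770 |

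Events and HR are those under the SAP rule.

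| No treatment effect, missing in control only | HR, SAP rule | Rejection, SAP rule | HR, comparator | Rejection, comparator |
|---|---|---|---|---|
| 5% | 0.986 | 0.114 | 1.005 | 0.100 |
| 10% | 0.977 | 0.117 | 0.997 | 0.102 |
| 20% | 0.955 | 0.141 | 0.997 | 0.100 |

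With no missing data, null rejection is 0.101. Simulation error on the rejection rates is about 0.006. Equal missingness leaves the HR where it was and costs events. The one-sided case shows that it is the selection on outcome, not the loss of subjects, that moves the HR. PFS and the fix proposed below were not simulated.

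**The case against.** The strongest reply is that the rule will rarely be used. Central review must confirm measurable disease before randomization (Protocol 4.1 and 6.8, SAP 4), and Appendix 5 defines that as at least one target lesion. A randomized subject without a central baseline target should be exceptional. This stands for the primary analysis. It protects less where mRECIST is applied to investigator measurements, because the central check does not guarantee that those exist.

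Second, a reader might infer that the rule biases the primary hazard ratio. The documents do not support that. Baseline scans are taken before randomization and central review is blinded, so imbalance would arise mainly by chance. If 5 of 100 subjects were affected, the chance that all were in control is C(50,5)/C(100,5) = 2.8%; for 10 it is about 0.06%. The control-only rows above are a deliberate extreme.

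Third, one might call the rule a flat contradiction of the PFS definition. A censoring rule may limit how a definition is applied, so the fairer word is inconsistent: subjects with the same kind of evidence are treated differently, and no reason is given.

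Fourth, counting later events while crediting event-free time has a cost of its own, since growth from baseline cannot be assessed. This stands in part. Appendix 5 refers progression to the smallest sum since treatment started, so growth from a post-baseline nadir can be read, but some progression may be found late.

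**Conclusion.** The point holds as a minor flaw. The rule makes censoring depend on the outcome and drops valid later progressions and PFS deaths that SAP 7.2.1, 7.3.1.2, 7.3.2, 7.5 and Protocol Appendix 5 would lead one to count, or to censor later. The expected effect on the primary analysis is very small. The investigator-measurement analyses are more exposed, by an amount the documents do not allow one to estimate.

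With equal missingness, the cost is lost events and a first-scan event rate raised by 0.7 to 1.4 percentage points at an assumed 5% to 10% missing, and by less if progression is harder to see without baseline targets. Bias in the hazard ratio needs unequal missingness, for which the documents offer no mechanism.

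Two further readings go too far. Affected subjects are not removed from the trial: they stay in OS and in the response-rate denominators. And although about 91% of deaths would fall after week 6 at an OS median of 10.7 months (about 86% at 6.5 months), that is a share of all deaths. It is not the share of PFS events lost, because many of those deaths would follow progression.

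**What to change.** Rewrite SAP 7.3.1.1 for subjects with missing baseline target measurements:

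- Count progression at any assessment if it rests on a new lesion, on unequivocal non-target progression, or on growth of at least 20% from the post-baseline nadir where that was measured.
- Otherwise censor TTP and PFS at the last assessment at which those lesions were read.
- Count death from any cause as a PFS event.
- Keep the subject non-evaluable for objective response.
- State whether the rule applies when one target lesion lacks a baseline measurement or only when all do.

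Add a TTP and PFS sensitivity analysis that censors all such subjects at randomization whatever their outcome, and report the number affected by arm for the central and the investigator data.

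The cost is a few lines of SAP text and programming and one extra set of outputs. It needs no new data. The remaining weakness is late detection of some target-lesion progression, which the sensitivity analysis addresses.
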